Protocol Title page

NCT number: NCT03428815

Official Title: Effects of Temperature Control Liner Materials on Long-Term Outcomes of Prosthesis Use

Document Date: January 15, 2020

The protocol has been approved by the responsible Institutional Review Boards. Study subjects are asked by the principle investigators to provide informed consent in accordance with human-subjects protection regulations.

**Subjects:** Subjects are recruited from the community at two sites, in Chester, PA, and Pittsburgh, PA. Inclusion criteria are the use of a prosthesis with liner suspension, at least one year of prosthesis use, a well-fitting socket, the ability to walk with the prosthesis outdoors without notable limitations (K-Level 3), stable weight, and absence of acute medical conditions that would temporarily affect the ability to use prostheses. Exclusion criteria are use of a non-standard liner size, known allergies against liner materials, and any inability to understand the protocol and to comply with the associated tasks, such as maintaining a log of days when the prosthesis could not be used.

Power analysis was based on the cross-over statistical methods above and previous literature and One-sided determination. Halsne, et al. , in an analysis of 12-month step activity data in participants with trans-femoral amputation reported that the average change in step activity scores for subjects in the hot and cold months of the year was significantly higher than in the moderate temperature months of the year corresponding to an effect size of 0.47. This effect size and a sample size of 50 subjects, results in 85% power to detect significant differences.

The assumed effect size would equate a difference in prosthesis utilization of four days per year if the average yearly number of days with prosthesis use has a standard deviation of 10 days. Irrespective of the statistical significance of such an effect, every day of work absence has a relevant economical effect to the employee and the employer. Given the duration of the study and the potential reluctance of subjects to change their liner type, it is anticipated that up to 9

subjects (18%) do not complete the protocol, bringing the statistical power to 80%. Comparable prospective intervention studies in the past have utilized sample sizes between nine and 20.

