Subjects are asked to continue their regular activities of daily life while wearing the new liner, and to make a note of any days during which the prosthesis could not be used due to residual limb health issues, as a redundancy to the step counter data. About every two weeks, a member of the research team will schedule a 5-minute appointment with the subject to read out Stepwatch data. Subjects are not required to come to the research site for the respective appointments, which may be scheduled at their homes or places of work according to subjects’ preferences. While the Stepwatch monitor can store up to 50 days of data, two-week-intervals have been chosen to mitigate the adverse effects of possible equipment malfunction or application errors. Any adverse events or other unsolicited reports will be recorded as they occur.

Every six weeks, appointments are scheduled to conduct the 2MWT, complete sections “About the prosthesis”, “Specific Bodily Sensations”, “Ability to Move Around”, “Satisfaction with particular Situations”, and “Importance of different aspects” of the PEQ, and read out step data.

At the 6-month appointment, after completing 2MWT and PEQ, subjects turn in their two study liners and receive two new liners, representing the respectively other variety. Following a short rest, subjects will complete the 2MWT and PEQ once more before the test day is concluded while wearing the new liner.

The 12-month appointment marks the end of the data collection for this study. Individuals blinded to liner type will perform all data collection.

Subjects receive a compensation of \$30 per site visit for a total compensation of \$270. This payment schedule is intended to reduce the occurrence of drop-outs.

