***Outcome Variables:*** The main outcome variable is prosthesis utilization and is operationally defined as “total step count per time” and as the “number of days with prosthesis use per time”. Prosthesis utilization is the clinically most relevant variable, as it describes the extent to which a person’s limb loss affects their social and economic participation. To determine the number of days of prosthesis use, self-reported information will be evaluated along with step count data. A day without substantial prosthesis use will be assumed if the daily step count is below the 20th percentile for the average daily step count of the respective individual over the full year. Only if both methods agree on the number of dates without prosthesis will the information be used for analysis in order to reduce the errors caused by inaccurate memory or by malfunctioning equipment.

Secondary outcome variables will be “Step count bouts per time unit”, “Two-minute walk distance”, “Prosthesis function rating”, “Well-being rating”, “Mobility rating”, and “Satisfaction rating”, the latter four of which are based on question groups 1, 2, 4, and 5 of the PEQ respectively. Analyzing those variables will allow a more comprehensive understanding of the effects of PCM liners and may inform the hypotheses of subsequent studies investigating their function mechanisms.

Depending on the eventual sample composition, it may be possible to extract incidental findings on the effects of demographic and anthropometric factors on measured outcomes with the

different liners. Any such results may be useful as pilot data for subsequent studies to further investigate the utility of PCM in prosthetics.

Several possible comparison variables are deliberately not included in this clinical trial.

Monitoring changes in liner temperature or material properties during use would necessitate the use of additional data collection equipment, which would be likely to interfere with the regular use of the liners and thus pose a bias to the measured data. Also, it is unclear how temperature data should be interpreted (e.g., whether lower temperatures are always better than higher, or steady temperatures better than fluctuating) to become clinically meaningful. It is anticipated that the findings of the present study motivate subsequent research to investigate the function mechanisms of PCM liners and to better explain the results of this study.

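### The 20th-percentile step rule flags about 73 days a year for nearly everyone, so the required agreement with the log would almost never occur and the days-of-use outcome would be lost

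*Combined protocol and SAP*

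**What the plan says.** The Outcome Variables section gives the main outcome, prosthesis utilization, two operational definitions: total step count and "number of days with prosthesis use per time". The second is built in two steps.

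- **Step rule.** "A day without substantial prosthesis use will be assumed if the daily step count is below the" 20th "percentile for the average daily step count of the respective individual over the full year".
- **Agreement rule.** "Only if both methods agree on the number of dates without prosthesis will the information be used for analysis". The stated aim is to limit errors from faulty recall and monitor failure.

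The Methods section describes the log: subjects are to "make a note of any days during which the prosthesis could not be used due to residual limb health issues". No tolerance, time window, fallback for disagreement or treatment of zero counts is given.

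The power paragraph under Subjects illustrates the assumed effect as "four days per year if the average yearly number of days with prosthesis use has a standard deviation of 10 days".

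**The concern.** A percentile taken from a person's own daily counts, and then applied to those same counts, fixes the share of days below it. The yearly number of flagged days is therefore set by the rule and says almost nothing about how often the prosthesis was not worn.

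The agreement rule turns this weakness into a loss of data. One source is pinned near 73 days. The other counts days lost to limb problems in outdoor walkers with well-fitting sockets, where few such days are expected. If the two numbers must match before the data are used, almost no subject contributes. If the rule is relaxed once this is noticed, a main-outcome definition is chosen after the data have been seen.

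**Working it through.** The plan states no figure for the number of days its rule will flag, so there is none to reproduce.

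**Inputs from the document.** Individual 20th percentile over the full year, and agreement on the number of dates (Outcome Variables); log limited to limb-health days (Methods); SD of 10 days and 50 subjects (Subjects, power paragraph).

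**Assumptions, not in the document.** 364 or 365 monitored days; lognormal daily steps with log-SD 0.3 to 1.0; zero steps on true non-use days; on average 6 versus 4 such days per half-year (10 a year); an accurate log. Non-use varies between people either as Poisson or as gamma-Poisson with a yearly SD of about 10.5 days.

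**1. Days flagged per year.** 0.20 x 365 = 73. Simulation at log-SD 0.5, with a fixed number of zero-step days inserted and *flagged* meaning strictly below the cut:

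| True zero-step days | Flagged days (range) |
|---|---|
| 0 | 71–73 |
| 10 | 72–73 |
| 40 | 72–73 |
| 73 | 73 |
| 74 or more | 0 |

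At 74 or more zero days the percentile itself is 0 and nothing lies below it. An accurate log would then also disagree with the step rule.

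**2. Spread between people.** The step-rule count has an SD of 0.14 to 0.19 days with Poisson non-use. With true SD about 10.5 it is 1.6 to 2.5 days (up to 2.8 in a repeat run), produced by the rare people whose count collapses to 0. The plan's illustration uses 10 days.

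**3. Agreement on the yearly number.** Take the log count as negative binomial with mean m and variance 10² = 100, and compute the probability that it equals 73:

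| Mean logged days m | P(log = 73) | Expected agreeing of 50 |
|---|---|---|
| 4 | 0.00015 | 0.007 |
| 10 | 0.00006 | 0.003 |
| 20 | 0.00004 | 0.002 |
| 40 | 0.0005 | 0.026 |
| 73 | 0.040 | 2.0 |

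A tolerance of 5 days either way still gives at most 0.7% for means up to 40. Direct simulation with 10 true days gives 0 of 100,000 (Poisson) and 11 of 100,000 (gamma-Poisson). With a mean of 40 true days and log-SD 0.6 it gives 0 and 0.39%.

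**4. Shorter windows.** The plan names none. With the same assumptions, agreement is at most 0.015% per half-year, 0.02% to 0.24% per six weeks and 7% to 8% per 14-day read-out. For a fortnight with no true non-use and independent days, the chance of no flagged day is 0.8^14 = 4.4%.

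**5. Other readings.**

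- *20% of the person's mean.* Against 10 true days this flags 10.1, 12.7, 27.6 and 55.0 days at log-SD 0.45, 0.6, 0.8 and 1.0.
- *Agreement date by date, percentile kept.* With an accurate log, the standardized liner difference is 0.53 to 0.64, against 0.52 to 0.64 for true non-use, so nothing material is lost. But the percentile checks little: a wrongly logged date falls below the cut with probability (73 − 10)/(364 − 10) = 17.8%.

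**The case against.** The strongest reply is that the sentence may not mean what it literally says. A person has one average over the year, and a single number has no percentile; 20% of the average may have been intended, and then the fixed 73 days disappear. Date-by-date matching also fits the stated purpose of catching recall errors and monitor failures, and under that reading almost nothing is lost. Both points stand as possible intentions. The text nevertheless says percentile and number of dates, and an outcome definition whose readings run from unusable to workable needs correcting in either case.

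Other points stand in part:

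- **Window.** Fortnightly matching raises agreement to 7–8%, or 16–17% with an assumed day-to-day autocorrelation of 0.5. Most data are still lost.
- **Log scope.** The Subjects section describes the log without restricting the cause, and the Methods section also asks for daily notes on limb or fit problems. The scope is inconsistent, but a broader log would still rarely reach 73 days.
- **SD comparison.** The 10-day SD is only an illustration, and only the yearly total is pinned. The split of flagged days between liners can still carry information. If the liner changes only zero-step days, the standardized difference is weak (0.20–0.22); with an assumed 5% rise in steps on use days it becomes 0.53–1.22. The plan does not analyse the step rule alone, so this does not rescue the outcome.
- **Reach.** Total step count is unaffected, and the 0.47 effect size behind the sample size does not come from days of use.

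**Conclusion.** The concern holds, and the definition must be corrected. That about 73 days are flagged follows from what a percentile is; it does not depend on the assumed step distribution, apart from the collapse to 0 when more than 20% of days have zero steps. That agreement almost never occurs rests on matching totals and on logs well short of 73 days. For mean logged or true non-use of up to 40 days a year, yearly agreement stays at or below about 0.4% in every setting tried. The consequence is confined to one of the two main-outcome definitions, but that is the one the plan uses to express the benefit in days.

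**What to change.** Amend the Outcome Variables section before the list linking serial numbers to liner type is opened.

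1. **Cut-off.** Replace the within-person percentile with a threshold that can vary with true non-use: either zero steps (or a stated near-zero count), or fewer than 20% of the person's median count over days with any steps. Name one as primary and the other as sensitivity. If 20% of the person's average was meant, say so.
2. **Agreement.** Require log and step data to agree date by date, and state how dates flagged by only one source are handled. Describe the log's scope in the same words throughout.
3. **Check.** Examine the chosen cut-off on step data pooled over liners, still blinded.

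The cost is a few sentences; the step data and log are already being collected. The drawback is that a proportional cut-off over-flags when daily steps vary widely. Against 10 true days, 20% of the median flags 10.1, 11.3, 17.9 and 29.0 days at log-SD 0.45, 0.6, 0.8 and 1.0, which is the same as or fewer than 20% of the mean. A zero-step cut-off avoids this but misses days of very brief use.

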A steady state within either of the interventions will be assumed, yet it will be possible to detect any baseline drift or seasonal fluctuations with the proposed repeated measures design. Previous studies have used a repeated measures design to investigate the reliability of outcome measures, such as the Locomotor Capabilities Index and the Two-Minute-Walk test. The Prosthesis Evaluation Questionnaire (PEQ) has been validated in that fashion as well.

Missing values are possible due to drop-out and intermittent non-compliance with the data collection schedule. This would not invalidate “year-on-year” comparison of the remaining data sets. Provided that baseline characteristics can be sufficiently described by existing data, it may also be possible to interpolate and extrapolate missing data points with some accuracy.

Despite the long duration of the data collection, the intervention itself will have a comparably low burden on the subjects’ daily lives, which is expected to make participation appealing to a wide range of potential subjects who are targeted by online and offline postings.

**Methods:** The protocol utilizes a double-blind longitudinal cross-over research design. A sample of trans-tibial prosthesis users is randomly assigned to one of two groups. While subjects in one group receive PCM liners, the members of the other group are fitted with regular gel or silicone liners. After six months, the first group receives conventional liners (and turn their PCM liners in) and the second group receives PCM liners (Table 1). Prostheses in either group are equipped with activity monitors, and participants are asked to keep daily notes of any perceived issues with their residual limb or socket fit. In regular intervals, subjects’ physical performance capabilities and prosthesis-related quality of life, including limb and overall health, is assessed using standardized methods.

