**Table 1: Schedule of enrolment, interventions, and assessments**

	STUDY PERIOD					
	Enrolment	Allocation	Post-allocation			Close-out
TIMEPOINT	$-t_1$	Jan 15 or Jul 15	Every 6 weeks	6 months	12 months	12 months
ENROLMENT:						
Eligibility screen	X					
Informed consent	X					
Liner size determination	X					
Allocation		X				
INTERVENTIONS (Randomized sequence):						
PCM liner			↔			
Placebo liner				↔		
ASSESSMENTS:						
Demographics, Anthropometrics	X					
Two minute walk (2MWT) distance			X			X
PEQ Scores			X			X
StepWatch activity data			X			X

Comparing liners over the duration of six months allows detecting short- and long-term effects of the different approaches, including effects due to seasonal outdoor temperature changes, material abrasion and fatigue, and potential unsustainable material properties (i.e., diminished temperature control capabilities of the PCM). In order to cover a comparable portion of the year regarding climatic conditions, the protocol is started at one of two dates only: Mid-Winter (around January 15th) or Mid-Summer (around July 15th). Any possible washout period after changing liners is expected to be completed well within the first assessment intervals , so that unbiased data can be compared for all the listed assessment points for either liner.

Randomization is performed by the study statistician, using proc survey select available in SAS version 9.4. in a block randomization scheme with lengths of 2 and 4. Blocks length is unknown to the clinical personnel. This block design assures a balanced allocation in the groups and reduces the chance that testing personnel will be able to guess the next intervention group assignment. This, in turn, serves to minimize bias in participant allocation to the intervention group at the beginning of the study.

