Patterns of association between descriptive measures (i.e., demographic and diagnosis characteristics) and intervention outcomes will be examined using paired t-tests, chi-square tests with Fisher's exact, correlation analyses (and regression analyses, as appropriate). From these analyses, critical demographic and clinical characteristics will be identified that will be controlled for in the statistical models and incorporated into the design of future controlled clinical studies. Data will be analyzed according to study group membership regardless of study completion. However, missing data patterns will be examined and reasons described for attrition and missing data because such patterns may be informative for identifying systematic biases in future studies. The Kolmogorov-Smirnov test will be used to verify the normality assumption and if it is violated appropriate transformations will be considered. Correction for multiple testing will be by adjusting p-values using the Benjamini-Hochberg method. Prior to formal statistical analysis, data will be compared across treatments to check if they are comparable. If differences exist, baseline demographic effects will be taken into account in mixed effects models. The correlation among repeated measures will be examined and adjusted appropriately such as unstructured, confound symmetry, or auto-regressive.

Outcome data are collected at baseline, 1.5-month, 3-month, 4.5-month, and 6 months and repeated at the 2nd half-year. The effect of intervention, time, and group\*time interactions will be evaluated. Baseline data for key variables will be compared between randomization groups, and if they are different, a random intercept mixed effect will be used. Mixed effects modeling techniques will be used for the repeated measures. Since mixed effects models do not assume a balanced design, subjects who do not have data (dropouts) on all 10 time points will still be

included in the analysis (intent to treat). It will be tested if scores for the intervention are significantly different from the control condition's scores.

Possible additional analyses include a more detailed investigation of prosthesis utilization over time by comparing seasons, months, weekdays, or hours of day within and across interventions. Furthermore, it may be possible to analyze covariates that predict prosthesis utilization, including anthropometric and demographic data.

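### The liner model has no start-date or calendar term, so annual-season variation stays in the error of the comparison

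*Combined protocol and SAP*

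**What the plan says.** The text after Table 1 fixes two start dates, for a climatic reason: "In order to cover a comparable portion of the year regarding climatic conditions", "the protocol is started at one of two dates only", in mid-winter or mid-summer. Under Methods, "After six months, the first group receives conventional liners" and the second group receives PCM liners.

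Under Statistical Plan and Data Analysis the visits are set out in study time: "Outcome data are collected at baseline, 1.5-month, 3-month, 4.5-month, and 6 months and repeated at the 2nd half-year", ten points in all. The terms to be evaluated are given as "The effect of intervention, time, and group" by time interactions, in a mixed effects model. No start-date, season or calendar term is named. Comparisons of seasons and months are listed only as possible additional analyses.

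Randomization is "in a block randomization scheme with lengths of 2 and 4", with no stated stratification by start date. On missing values, the text before Methods says: "This would not invalidate “year-on-year” comparison of the remaining data sets". The same part says that seasonal fluctuations can be detected, but not that the liner comparison is adjusted for them.

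**The concern.** A January starter wears the first liner from January to July and the second from July to January; a July starter does the reverse. Liner and calendar half-year can be separated only across subjects, through the mix of start dates and sequences. Study month does not make that separation: at month 0 it pools subjects in mid-winter with subjects in mid-summer, and at month 3 it pools spring with autumn. An annual cycle in step counts averages out of the study-month effect and remains in the residual.

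The plan's existing covariate provision does not cover this. It concerns demographic and clinical characteristics, and start date entered only as a subject-level main effect would cancel from a within-subject contrast. Its interaction with time is what is needed.

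The year-on-year safeguard is not available either. With 12 months of follow-up, each calendar date is seen once per subject, under one liner, so there is no second year to match against when data are missing.

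At stake is the precision of the main comparison, and a later choice between adjusted and unadjusted liner estimates if the adjustment is not prespecified.

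**Working it through.** **The plan's own figure.** The power paragraph gives effect size 0.47, 50 subjects, a one-sided test and 85% power, falling to 80% with 41 completers. Alpha is not stated; 0.05 is assumed here. A paired t calculation with 0.47 as the standardized within-subject difference gives 94.9% at n = 50 and 90.5% at n = 41, so the 85% is not reproduced. An effect of 0.385 would give 85.0% and 78.1%. That is a separate matter; both effects are carried below.

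**Model for the half-year difference.** Let s be the January–July minus July–January difference, in SDs of the within-subject liner difference. The documents do not give s, so a range is assumed. For subject i, period 1 minus period 2 is

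d = ±τ (sequence) + period effect ± s (start date) + error, with error SD 1.

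If a share p starts in January and start date is not in the model, the error variance becomes 1 + 4p(1 − p)s². At p = 0.5 this is 1 + s². Power is the noncentral-t probability with noncentrality 0.47√n / √(1 + s²) and n − 2 degrees of freedom. For n = 41 and s = 0.47: 0.47 × 6.403 = 3.009; √1.221 = 1.105; 3.009 / 1.105 = 2.72; power 0.849.

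| s | Error variance | Power, n = 41, no term | Power, n = 41, with start date by period (1 df) |
|---|---|---|---|
| 0 | 1.00 | 0.905 | 0.905 |
| 0.25 | 1.06 | 0.889 | 0.905 |
| 0.47 | 1.22 | 0.849 | 0.905 |
| 0.75 | 1.56 | 0.764 | 0.905 |
| 1.0 | 2.00 | 0.672 | 0.905 |

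With the effect set to 0.385, power at n = 41 without the term is 0.759, 0.698 and 0.526 for s = 0.25, 0.5 and 1.0, against 0.780 with it. With a 70:30 split and effect 0.47, it is 0.852 at s = 0.5 and 0.704 at s = 1.0. If everyone started on the same date, nothing would be lost.

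**Form of the loss.** If sequences are not balanced within start date, the estimate itself is noisier. If they are, s nearly cancels from the estimate but stays in the residual, and the test becomes conservative: simulated one-sided error is 3.3% at s = 0.5 and 1.1% at s = 1.0. In simulation the mean estimate stays at 0.47.

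**How large s could be.** Take an annual cosine peaking L months after the start date. The difference between the two half-year visit means is 0.966 × sin(30° × L) times the amplitude: zero at L = 0, 0.25 at half a month, 0.48 at one month. At a one-month lag, s = 1.0 needs an amplitude of about 1 / 0.48 = 2.1 SD.

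**A symmetric annual curve still matters at visit level.** With L = 0, s is zero, but at each visit the two start groups deviate from the visit mean by ±A·cos, where A is in visit-level residual SDs. Over months 0, 1.5, 3, 4.5 and 6, cos² is 1, 0.5, 0, 0.5 and 1, mean 0.6. With 50 subjects, 10 visits and subject intercepts, residual degrees of freedom are 500 − 50 − 9 − 1 = 440. The residual variance is then 1 + (500 / 440) × 0.6A² = 1 + 0.68A². The reported SE is too large by √1.17 = 1.08 at A = 0.5 and √1.68 = 1.30 at A = 1.0. With sequences balanced by start date, the actual variability of the estimate barely changes. Start date by study time removes the excess; a single start-date-by-period term does not, since the period means are equal here.

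**The case against.** The strongest reply is that the start dates were chosen to deal with climate. Changing liner at mid-winter or mid-summer gives both half-years the same temperature range, and any curve symmetric about those dates has equal half-year means. That stands, and it limits s to an asymmetric or lagged remainder. It is still not an adjustment, and it does not stop study month from pooling opposite seasons at each visit.

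A reader might take 0.47 as the trial's own estimate of s and conclude that the omission costs 1 − 1/1.22 = 18% of the information, as much as the planned drop-out. The documents do not support this. The 0.47 contrasts hot and cold months with moderate months. That pattern repeats every six months, so both start groups are in the same category at the same study visit: study month absorbs it, and its half-year difference is zero. The 0.47 row in the table is only a point in an assumed range.

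Other limits also stand. With the effect taken as 0.47, power at 41 completers stays above the planned 80% until s approaches 0.75; with the effect that reproduces 85%, it starts at 78% and falls from there. Blocks of 2 and 4 filled one start date after the other would already nearly balance sequences within date. The start-date split is not given, and time is not formally defined; study month is a reading of the only scale listed.

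**Conclusion.** The point holds as a matter of efficiency. As written, the model leaves annual-season variation in the error of the liner comparison, and a term built from dates already recorded removes it. Under the assumptions above, the loss of power at 41 completers is about 2 points at s = 0.25 and 6 points at s = 0.47. The losses of 14 and 23 points at s = 0.75 and 1.0 are unlikely given the choice of start dates. The true size is unknown, and the loss arises only if both start dates are used.

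A reader might also infer that the liner estimate is biased. That is not shown: with random drop-out it stays centred on the true value, and a shift would need attrition that differs by start date and sequence, for which the documents give no evidence.

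**What to change.** - In the primary mixed model, prespecify start date (January or July) and its interaction with study time, and state whether time means study month or calendar time. The minimum is start date by period (1 df), which removes a half-year difference but not opposite seasonal patterns within the half-years. With categorical visits the full version takes about 9 to 10 df.
- Run the existing lists of blocks of 2 and 4 separately for each start date.
- Replace the year-on-year sentence with a statement that incomplete subjects are compared after adjustment for calendar time.

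The cost is SAP wording, a second block list and a few degrees of freedom. In the 1-df calculation, power at s = 0 is unchanged to three decimals.

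### The model sentence does not tie the PCM-versus-control test to an estimable crossover term; read with group as sequence, the liner term is aliased or loses power

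*Combined protocol and SAP*

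**What the plan says.** Under Methods, "The protocol utilizes a double-blind longitudinal cross-over research design". Subjects are randomised to one of two groups, and "After six months, the first group receives conventional liners (and turn their PCM liners in) and the second group receives PCM liners". In that usage a subject stays in one group throughout and wears both liners.

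Under Statistical Plan and Data Analysis, the only statement of model terms is "The effect of intervention, time, and group" by time interactions. The same section says:

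- "Outcome data are collected at baseline, 1.5-month, 3-month, 4.5-month, and 6 months and repeated at the 2nd half-year", which makes ten time points. It does not say whether time is ten categories, five visits within each half-year, or a linear trend.
- "Data will be analyzed according to study group membership regardless of study completion".
- "Baseline data for key variables will be compared between randomization groups", and "if they are different, a random intercept mixed effect will be used". The random subject effect therefore depends on a baseline finding.
- "It will be tested if scores for the intervention are significantly different from the control condition's scores". This is the intended comparison, but no model term or contrast is named for it.

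The section lists unstructured, compound-symmetry and autoregressive correlation as options. The power paragraph, under Subjects, says that power was based on crossover methods and a one-sided test. It gives 85% with 50 subjects and 80% if 9 drop out.

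**The concern.** In a two-period crossover the liner worn is an exact function of sequence and half-year. A term that crosses sequence with time over the whole year therefore competes with the liner effect or absorbs it. If group means sequence, the three listed terms can leave the intervention term inestimable, spread the liner effect over a multi-df interaction, or test it with an inflated standard error. If group means the liner being worn, or if time is coded within half-years, the difficulty can disappear.

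The plan does not choose between these readings. At stake is whether the main comparison is fixed in advance, and whether the stated power belongs to the model that will be fitted.

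**Working it through.** **Inputs.** From the documents: two sequences, ten time points (months 0, 1.5, 3, 4.5, 6 and 6, 7.5, 9, 10.5, 12), effect size 0.47, 50 subjects (41 completers), stated power 85% (80%). Assumed: alpha 5% one-sided (the plan gives the side but not the level), equal sequences and complete data.

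**1. The plan's own power.** A paired one-sided test with d = 0.47 by noncentral t gives 94.9% (n = 50) and 90.5% (n = 41), not 85% and 80%. A within-subject correlation of about 0.3, which the plan does not state, gives 86.9% and 80.3%. That is a separate matter. Below, power is anchored on the stated 85%, so the standardised effect is 1.645 + 1.036 = 2.681. For a liner variance R times that of the crossover contrast,

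Power = Φ(2.681/√R − 1.645).

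**2. Group as sequence, time as ten categories.** Group, time and group by time span all 2 × 10 = 20 cell means. The fixed-effects rank is 20 without a liner column and 20 with it, so the separate intervention term has 0 df. With eight six-week step-count intervals (an assumed layout) the ranks are 16 and 16. The group-by-time test has 9 df and noncentrality 2.681² = 7.19, so its power at 5% is 41% (35% from the 80% anchor). A 1-df liner contrast formed from the same 20 cell means has R = 1.0 and keeps the full 85%.

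**3. Group as sequence, linear 12-month trend, compound symmetry.**
- Within a sequence, the centred liner indicator is ±0.5, with sum of squares 10 × 0.25 = 2.5, or 5.0 over both sequences.
- Centred months have sum of squares 2 × (36 + 20.25 + 9 + 2.25) = 135. Their cross-product with the liner indicator is 2 × 0.5 × (6 + 4.5 + 3 + 1.5) = 15.
- The trend removes 15²/135 = 1.667 per sequence, 3.333 in all. What remains is 1.667, so R = 5.0/1.667 = 3.0.
- Power = Φ(2.681/1.732 − 1.645) = Φ(−0.097) = 46% (42% from the 80% anchor).

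This includes a group main effect, which the model sentence does not list. Without it, R is 2.16 at within-subject correlation 0.5 and 2.67 at 0.8, so power is 57% and 50%. With the assumed eight intervals and the group main effect, R = 4.2 and power is 37%.

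**4. Conditions that soften the loss in step 3.**
- AR(1) with parameter 0.5 to 0.8: across the two layouts the standard-error factor is 1.04 to 1.42, so power is 82% to 60%.
- Liner effect varying between subjects, with variance τ² as a multiple of the residual variance (assumed 0.25 to 1), ten visits: R = (1.2 + τ²)/(0.4 + τ²). This is 1.45/0.65 = 2.23 to 2.2/1.4 = 1.57, so power is 56% to 69%.

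**5. Readings with no loss (R = 1.0).**
- Group read as the liner being worn, with time centred.
- Time coded as visit within half-year, under compound symmetry.
- No sequence-by-time term.
- The 1-df contrast from the cell means in step 2.

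**The case against.** The strongest reply is that the plan intends the right test and can be read so as to deliver it. It lists an effect of intervention, says that intervention scores will be tested against control scores, and bases power on crossover methods. The word group is not used only for sequence: the randomisation paragraph under Methods speaks of an intervention group, and the blinding paragraph has results attributed to a group once the liner list is opened. Because no group main effect is listed, two main effects and their interaction is a fair reading of the sentence, with group meaning liner. The five time points repeated in the second half-year fit a visit-within-period coding.

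Most of this stands. It removes three stronger conclusions that a reader might infer:

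- That the trial has no main test. The comparison is stated, and even in the saturated model a 1-df contrast recovers it at full efficiency. Only the separate model term is lost.
- That this is a parallel-group model. Intervention is listed apart from group, and the time points span both half-years.
- That the plan compares the two groups over the whole year, where the liner effect would cancel. The sentence on study group membership is an intention-to-treat statement, not a model.

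It does not remove the ambiguity. References to randomisation groups and to first and second groups point to sequence, and ten time points as categories is an ordinary coding. Each harmless reading needs a choice that the plan does not record.

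**Conclusion.** The primary model is under-specified for a crossover. The intended PCM-versus-control test is stated but not tied to an estimable model term, and no period or sequence effect is named.

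The size of the consequence depends on the reading. With group as sequence and ten categories, the intervention term cannot be estimated and the omnibus interaction test has about 41% power. With a linear trend and compound symmetry, 85% falls to about 46–57%, and by less under AR(1) or with subject-by-period variance. On the other readings nothing is lost. These figures assume a one-sided 5% level and rest on the stated 85%, which does not follow from its stated inputs alone. Starting from d = 0.47 paired (about 95%), the same R = 3.0 gives Φ(0.47√50/√3 − 1.645) = 61%.

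This should be fixed as a free improvement. It does not show that the trial cannot answer its question.

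**What to change.** Replace the model sentence with a crossover mixed model:

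- **Fixed effects:** liner assigned in the period (PCM or conventional), period, randomised sequence, and visit within period.
- **Random effects:** a subject effect that does not depend on a baseline comparison, and a subject-by-period term.
- **Main test:** the 1-df liner effect.
- **Secondary test:** liner by visit within period, for change over time.
- **Exclusion:** no sequence-by-time term in the main model. In this design the sequence-by-period interaction is the liner effect.

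Define group as the randomised sequence wherever it appears. State that intention to treat means analysis by the liner assigned in each period by the randomised sequence.

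Under compound symmetry the liner contrast then has R = 1.0, so the stated 85% and 80% carry over to the fitted model to the extent that they are right. The cost is a wording change before analysis, with no extra data or subjects.
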